**(2) PURPOSE OF STUDY:**

The purpose of the study is to monitor longitudinal changes in brain structure and function between the preseason and postseason, in a population of soccer playing athletes wearing the Device and compared to a similar population not wearing the device. Secondly, the purpose

is to determine the protection of the device relative to amount and magnitude of sustained head impacts.

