### **Injury Surveillance**

*Device and Compliance Acceptance:* The study coordinator will be responsible for providing the appropriate intervention (device or no-device) to each team based on their assignment prior to the season onset. At first fitting of the collar a registered vascular technologist will utilize ultrasound to ensure that the collar fits correctly and is activated as prescribed. Following the initial fitting, each athlete will receive adequate instruction on how to properly use the device on a daily basis. Throughout the season, the coordinator will make routine visits to each team to monitor the proper usage and fitting of the device, tracking the use of the device by each athlete individually. At the end of practice/game the device will be collected by the athletic trainer and/or stored in the athlete's locked locker. The device is NOT to go home with the athlete.

*New Concussion Surveillance and Follow-up:* Each participant will be provided with an X Patch accelerometer (X2 Biosystems; Seattle, Washington) The X patch adheres to the head, just behind the ear using an adhesive patch, as seen in the image below. .

X2 is a small and durable device that is attached to the back of the neck behind the ear to track impacts, and it stores data for uploading to a PC. This X2 accelerometer accurately measures the severity of impacts by converting data such as high impact collision into usable data outputs. X2 data will be used in final analysis to normalize the exposures to potential concussive events. All impacts of greater than 10 g-force will be recorded and utilized in the post-season analyses. No one besides those approved by this IRB protocol will have access to any data. If available, video of games and practices will be used to validate and confirm head impacts recorded by accelerometers.

concussion testing completed as part of the study, will be used in making any clinical decisions for return to play.

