***Statistical considerations.*** The data analysis will begin with a review of descriptive statistics for all major variables and all major subgroupings of variables in the data set. For the inferential methods, we will use a number of different generalized linear modeling techniques, including linear regression models. All analyses will be conducted using SAS® version 9.3 (SAS Inst, Cary, NC), or Mplus (Muthén, 2007). Initial analyses will be undertaken to inspect data for errors, inconsistencies, and incomplete information. This will include examining the data with simple frequency tables and dot plots for univariate data and scatter plots and multi-way dot plots for bivariate and multivariate data. Data anomalies that cannot be resolved by the Biostatistical/data management team will be sent as queries via

email to the project investigator for clarification and/or correction. During the verification process, outlying values will be corrected if necessary. Incomplete information will be corrected and the project investigator will receive updates. To summarize bivariate relationships among predictors and between predictors and outcomes, Chi-square of Fisher's exact test or Spearman's rank correlation coefficient, will be used, as appropriate. For reporting inferential statistics, such as differences in rates or means, 95 percent confidence intervals will be used extensively to quantify degree of clinical efficacy. Unless otherwise stated, statistical tests are considered two-sided and a .05 significance level is used. All models will be adjusted for potential independent predictor variables but will be limited to the number of predictors we can fit in a regression model while maintaining a valid and reliable model. Candidate predictors include amount of playing time, amount of practice time, previous mTBI, weight, age and height. Collinearity will be examined. Linearity assumptions will be checked and transformations examined. In those cases, a log transformation, polynomial terms, or restricted cubic splines will likely be used to relax the assumption of linearity in the regression models. We will remove the nonlinear terms or transformation only if the nonlinear test is non-significant with a  $p \geq .10$ . Additionally, overly-influential observations and distributional assumptions will be checked. Models will be interpreted graphically, predicted values will be examined, and appropriate significance tests will be utilized.

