***Statistical analyses.*** - Statistical analysis of outcomes measures will be done using SAS®, version 9.3 (SAS Institute, Cary, NC) and SPSS statistical software (SPSS Inc, Chicago IL). Comparisons between the testing conditions (collar vs. no collar) will be made using Analysis of Covariance, in order to control for time (pre vs post season) and condition (collar versus no collar). We will also conduct correlation analysis to test the association between imaging biomarkers (as described above) with the results obtained from the impact surveillance. The collision indices, including total number of collisions, number of collisions from front, back, left, right, top, bottom, G force, and timing of each collision will all be recorded and tested in the analysis. Secondary analysis to compare the intervention with no intervention and calculate the rates would involve a Poisson model, using an offset to account for the playing time and exposure to concussive impact for each of the study participants. We will calculate the rate and the associated 95% confidence interval. SAS®, PROC GENMOD will be used for analysis, which allows us to account for the fixed and random effects, use the appropriate link function, and the offset for amount of playing time exposure.

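### The plan allows the collar versus no-collar comparison to be adjusted for playing and practice time, which accrue after allocation, so it may not estimate the total device effect

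*Combined protocol and SAP*

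**What the plan says.** Section (9), Statistical considerations, sets a general rule: "All models will be adjusted for potential independent predictor variables but will be limited to the number of predictors we can fit". It then gives the list: "Candidate predictors include amount of playing time, amount of practice time, previous mTBI, weight, age and height". The last four can be taken at baseline. The first two cannot, if they mean time during the study season.

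The next paragraph, Statistical analyses, shows that they do mean that. The secondary Poisson model treats playing time as exposure accrued by each athlete, "using an offset to account for the playing time and exposure to concussive impact for each of the study participants". The same paragraph gives the device comparison: "Comparisons between the testing conditions (collar vs. no collar) will be made using Analysis of Covariance", with time and condition as the named terms.

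Section (8), Injury Surveillance, has the coordinator provide the device or no device to each team according to an assignment made before the season starts. The abstract describes the assignment as random. The control condition is simply no device, so athletes know their group.

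Section (2) gives two purposes. The first is the comparison of pre- to post-season brain change between groups. The second is "to determine the protection of the device relative to amount and magnitude of sustained head impacts". The plan does not say which candidate covariates belong to which purpose, and it does not describe a device comparison without playing and practice time.

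**The concern.** Random allocation protects a comparison of groups as allocated, adjusted if wished for variables fixed before allocation. Playing and practice time are fixed afterwards. An athlete who knows she is wearing a collar may play more or less, or be selected more or less often.

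If that happens, adjusting for playing time does two things. It removes whatever part of the device effect acts through participation. It also opens a non-causal path: if ability or aggressiveness drives both playing time and brain change, athletes with equal playing time in the two arms are no longer alike on that trait. The adjusted coefficient then answers neither purpose cleanly. It is not the total effect of assigning the collar, and without further assumptions it is not the effect at equal exposure.

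The stated limit on model size does not protect against this. Six candidates with up to 150 athletes is 150 / 6 = 25 athletes per predictor, so playing and practice time would probably not be dropped for lack of room.

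**Working it through.** The plan gives no effect size, SD or power calculation, so there is no figure to reproduce. The checks below show how large the effect could be under stated assumptions.

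**Inputs from the documents**
- Up to 150 athletes (section 6).
- Concussion rates of 0.36 per 1,000 and 4.5 per 10,000 athlete exposures (section 3).
- Testing: "statistical tests are considered two-sided and a .05 significance level is used".

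**Assumptions**
- 75 athletes per arm, treated as independent.
- Outcome and playing time in SD units.
- 40 to 80 exposures per athlete-season.
- The loadings and shifts given in each step.

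**1. Scale.** SE = sqrt(2/75) = 0.163 SD. The difference detectable with 80% power is (1.960 + 0.842) × 0.163 = 0.457 SD. Correlation within teams would raise both.

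**2. Direct route: the collar changes participation.** In a linear model,

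adjusted coefficient − total effect = −b × shift,

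where b is the within-arm slope of outcome on playing time and shift is the collar's effect on playing time. If an unmeasured shared cause loads 0.5 on each, b = 0.5 × 0.5 = 0.25. With a true device effect of zero, the approximate rejection rate is Φ(−1.96 + bias/SE) + Φ(−1.96 − bias/SE).

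| Shift in playing time (SD) | Bias (SD) | Bias / SE | Type I error |
|---|---|---|---|
| 0 | 0 | 0 | 5% |
| 0.1 | 0.025 | 0.15 | about 5.3% |
| 0.3 | 0.075 | 0.46 | about 7.5% |
| 0.5 | 0.125 | 0.77 | about 12% |

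Simulation of the last two rows (n = 150, 4,000 runs) gave bias of 0.076 and 0.124 SD, with rejection rates of 7.3% and 11.7%. The sign follows the signs of the shift and the loadings: a shift the other way gives the mirror image.

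**3. If playing time also acts on the outcome.** A second simulation assumed:
- a direct collar effect of −0.4 SD;
- a playing-time effect of 0.3 to 0.5 SD per SD;
- a shared cause present or absent;
- a 2.7% control concussion risk, halved by the collar.

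Adding playing time moved the collar coefficient by +0.05 to +0.11 SD when the collar lowered playing time by 0.2 SD, and by +0.13 to +0.30 SD when it lowered it by 0.5 SD. Part of this movement is the removed indirect effect.

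**4. Concussion route.** Expected concussed athletes = 150 × (1 − exp(−rate × exposures)).
- Lower end: 150 × (1 − exp(−0.00036 × 40)) = 2.1.
- Upper end: 150 × (1 − exp(−0.00045 × 80)) = 5.3.

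Suppose the collar halves the risk, a concussion costs 1.5 SD of playing time and worsens the outcome by 1 SD, and the control risk is 2.7% (0.00045 × 60 exposures). Adding playing time then moves the collar coefficient by −0.005 to −0.008 SD. That is about 5% of one SE at most (0.008 / 0.163), and opposite in sign to the movement in step 3.

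**The case against.** The strongest reply is that the plan does not commit to this adjustment. The variables are candidates. The ANCOVA paragraph names only time and condition, the ANOVAs for reaction time and oculomotor measures name no covariates, and neither does the voxel-based imaging analysis. This stands: a reader might infer that the device models will certainly contain playing time, and the text does not go that far. The general rule still covers all models, and nothing excludes these two variables.

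A reader might also infer that the device effect is biased. The documents do not show that. They give no figure for any effect of the collar on participation, and what they report leans towards a small one. In the Summary of Prior Work (section 3), the football study had similar total impacts by arm (16,983 versus 17,750, p > .05) and the hockey study had similar accumulated g-force. Those are proxies for playing time; the football sample was male and wore helmets. Athletes who stop playing are withdrawn (section 6), which narrows how far playing time can vary among those analysed. The larger shifts in the table are therefore sensitivity values, not expectations.

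Three other strong readings fail:
- Lost play after concussion is not a material route, because only about 2 to 5 cases are expected.
- Pre-season values are not ignored. They enter through the pre/post time factor, although they are not named as a covariate.
- An unadjusted analysis is not guaranteed a 5% error rate. Assignment is by team and the calculations treat athletes as independent. Playing and practice time might also absorb chance differences between team schedules, which is a real argument for showing an adjusted model somewhere.

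Finally, the statement that "X2 data will be used in final analysis to normalize the exposures to potential concussive events" concerns accelerometer data. Impact counts are not on the candidate list, and section (9) relates them to imaging in a separate correlation analysis.

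**Conclusion.** The point holds as a gap in specification. The plan permits covariates that accrue after allocation in its main device comparison, and it sets out no baseline-only version. Whether this distorts the result depends on whether the collar changes participation, which the documents do not quantify. With no change there is no bias by this route. With a shared-cause loading of 0.5, the bias is a quarter of the shift: well inside one SE for a 0.1 SD shift, and about three quarters of an SE for 0.5 SD. The direction cannot be fixed in advance. These figures rest on assumed loadings, 1:1 allocation and independent athletes. The case for changing the plan is that the remedy is cheap and keeps the two purposes apart, not that harm has been shown.

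Playing time as the offset in the Poisson model is an ordinary rate denominator and is not in question.

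**What to change.** In section (9), state that for the main collar versus no-collar comparisons covariates are limited to baseline variables: the pre-season value of the outcome, age, height, weight and previous mTBI. Where a repeated-measures model already carries the pre-season value as a response, it need not be added again.

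Report playing time and practice time by arm, so that any effect of the collar on participation can be seen. Keep models adjusted for either one as labelled secondary analyses under the second, exposure-related purpose. Leave the Poisson offset as it is.

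The cost is SAP wording. No new data are needed and no planned analysis is lost. The downside is that the main estimate is no longer exposure-adjusted, and it may lose some precision or some adjustment for chance differences in team schedules. The secondary models would still show both.

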**(1) ABSTRACT:**

Significant morbidity, mortality, and related costs are caused by traumatic brain injury (TBI). A simple, effective, and lightweight device worn by athletes or war fighters in the field, designed to mitigate TBI resulting from blast trauma or concussive events, would save lives, and the huge costs incurred for life-treatment of surviving victims. An externally-worn medical device (the Device) that applies mild jugular vein compression according to the principle of the Queckenstedt Maneuver, is being developed by Q30 Sports Science, LLC (Q30). Preliminary research suggests that the Device has the potential to reduce the likelihood of TBI. The currently developed collar (Smith 2009, Smith and Fisher 2011, Smith and Fisher 2011, Smith 2012) has been approved for studies in humans (IRB 2013-2240) and the results indicate safety for use during high demand and maximal exertion activities. Regarding safety, the externally worn collar is meticulously designed to mimic the body's own omohyoid muscle actions upon the jugular veins that will provide similar pressure and volume increases not to surpass that of a yawn or the mere act of just lying down.

This study will investigate the effectiveness of this device in high school athletes playing a non-helmeted sport such as soccer. Athletes participating in this study will be randomly assigned to one of two groups: 1) Device wearing during the season or 2) Non-device wearing during the season. This study will focus on the use and effectiveness of the device solely in females, as male football and hockey players have previously been investigated. All participants will be outfitted with an adhesive patch-like accelerometer (which will be placed behind the ear (*Xpatch-X2 Biosystems* [http://www.x2biosystems.com/x2\\_x\\_patch/](http://www.x2biosystems.com/x2_x_patch/)) which will measure the magnitude of every impact to the head sustained by the athlete. Effectiveness of the device will be determined via differences in longitudinal brain imaging and functional testing following competitive soccer participation. A subset of athletes who report a diagnosed concussion will also receive additional brain neuroanatomical and neurophysiological testing within a week following the diagnosed concussive event. At each of these time points participants will also undergo various neurocognitive assessments outlined below.

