D. fMRI and CO2 reactivity was performed on 12 adults before and after application of jugular vein compression. Results comparing before and after jugular vein compressions (with the collar) yielded no alterations in O2 uptake or glucose metabolism to any portion of the brain.(Fisher, Duffin et al. 2013).

E. An *in vivo* clinical trial was approved by CCHMC IRB and was completed in the Cincinnati Children's Hospital Human Performance Laboratory and Radiology Department (Study ID: 2014-5009; PI: [name]) An *in vivo* clinical trial was performed in hockey players of the proposed intervention device used during sporting competitions to test its effect in ameliorating neuroanatomical and neurophysiological changes to the brain using two widely accepted techniques [diffusion tensor imaging (DTI), and event related potentials (ERPs) utilizing electroencephalography.](Reches, Laufer et al. 2014) For athletes in the non-intervention group, radial diffusivity (RD, DTI parameter associated with white matter structural integrity(Song, Sun et al. 2003, Song, Yoshino et al. 2005)) increased significantly from pre-season to mid-season. By comparison, the athletes in the intervention group did not show a significant change in RD with similar accumulated g-force head impacts. In kind, ERP analysis showed concomitant changes in brain network dynamics in the non-intervention group—the level of change was strongly correlated with the accumulated g-force of the collisions, whereas the intervention group showed no significant change. These group differences indicate that mild jugular vein compression may provide protection from the detrimental effects of collisions and resultant brain injury. These prospective longitudinal data utilized an internal (*in vivo*) approach and demonstrate that it is possible to protect the brain from sports related head impacts.

F. An *in vivo* clinical trial was approved by CCHMC IRB and was completed in the Cincinnati Children's Hospital Human Performance Laboratory and Radiology Department (Study ID: 2015-2205; PI: [name]) The *in vivo* clinical trial was performed in football players implementing the proposed intervention device used during sporting competitions to test its effect in ameliorating neuroanatomical changes to the brain using evidenced by

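### For imaging, the ANCOVA names only time and condition, so the between-arm contrast in pre- to post-season change is not specified

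*Combined protocol and SAP*

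**What the plan says.** The Abstract states that "Effectiveness of the device will be determined via differences in longitudinal brain imaging and functional testing following competitive soccer participation". Section (2), Purpose of Study, gives the first aim as to "monitor longitudinal changes in brain structure and function between the preseason and postseason, in a population of soccer playing athletes wearing the Device", compared with similar athletes without it. The quantity of interest is therefore the difference between arms in pre- to post-season change.

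The only between-arm model that can cover imaging is in section (9), Statistical analyses: comparisons "will be made using Analysis of Covariance, in order to control for time (pre vs post season) and condition (collar versus no collar". Nothing else in section (9) completes it for imaging:

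- Statistical considerations: "Candidate predictors include amount of playing time, amount of practice time, previous mTBI, weight, age and height". The pre-season imaging value is not listed.
- Data Analysis: the voxel-based analysis is optional and exploratory, and looks for regions that differ between groups or that change over time. A between-group contrast of change is not named.
- Simple Reaction Time and Oculomotor Measures: group-by-time designs are written, but for those outcomes only.
- The mention of fixed and random effects belongs to the secondary Poisson rate model.

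On impacts, the same section says: "We will also conduct correlation analysis to test the association between imaging biomarkers (as described above) with the results obtained from the impact surveillance". It does not say whether this is pooled, done within arm, or tested as a difference between arms.

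**The concern.** The sentence cannot be run as it stands. It compares two conditions while controlling for condition, and both named terms are two-level factors, so the covariate that would make the model an analysis of covariance is never identified. At least three models fit the wording: an additive model on both visits, a group-by-time (change-score) model, and a post-season comparison adjusted for the pre-season value. They differ in what they estimate, in how they respond to baseline imbalance, and in power. Imaging is one of the bases on which effectiveness is to be judged, and the text leaves this choice open until after the data are seen.

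A secondary matter is the correlation with impacts. If it were read as evidence on the second aim, which "is to determine the protection of the device relative to amount and magnitude of sustained head impacts", then how arm is handled would decide what it shows. In the hockey study under Summary of Prior Work, electrophysiological results are described by arm: in the no-collar group "the level of change was strongly correlated with the accumulated g-force of the collisions, whereas the intervention group showed no significant change". Significance in one arm and not in the other is not a test of the difference between arms.

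**Working it through.** The plan gives a recruitment ceiling of 150 but no power, effect size, SD or pre-post correlation for imaging, so there is no planned figure to reproduce. What follows is illustrative.

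**Inputs.** From the plan: up to 150 athletes, two-sided 0.05. Assumed: equal arms of n = 75, or n = 60 because section (8) lets some athletes skip imaging; individual randomisation; SD of 1 at each visit; post-season effect d = 0.5 SD; pre-post correlation ρ = 0.5/0.7/0.9. Normal approximation throughout.

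**Step 1: what each model estimates.** With a systematic pre-season difference b, the arm difference is b before the season and b + d after it.

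- Additive time + condition: the condition term averages the two, [b + (b + d)]/2 = b + d/2. SE = √(2·((1+ρ)/2)/n), allowing for the repeated measures.
- Change score (group-by-time): d. SE = √(4(1−ρ)/n).
- Post-season value adjusted for pre-season value: d + b(1−ρ), which is d when b = 0. SE = √(2(1−ρ²)/n).

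**Step 2: power with b = 0.** At n = 75 and ρ = 0.5:

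- Additive: 0.25/√(1.5/75) = 0.25/0.1414 = 1.768; power Φ(1.768 − 1.960) = 0.424.
- Change score: 0.5/√(2/75) = 0.5/0.1633 = 3.062; power Φ(1.102) = 0.865.
- Baseline-adjusted: 0.5/0.1414 = 3.536; power Φ(1.576) = 0.942.

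| Model | n = 75, ρ 0.5/0.7/0.9 | n = 60, ρ 0.5/0.7/0.9 |
|---|---|---|
| Additive time + condition | 0.424/0.382/0.349 | 0.353/0.318/0.290 |
| Change score | 0.865/0.977/>0.99 | 0.782/0.942/>0.99 |
| Baseline-adjusted | 0.942/0.990/>0.99 | 0.885/0.970/>0.99 |

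A simulation (n = 75, ρ = 0.7, true effect 0.50) gave a mean additive estimate of 0.25.

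**Step 3: a 0.3 SD baseline imbalance with no device effect, n = 75.** Two situations must be kept apart.

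*Systematic imbalance* (groups differ in the population and stay apart, for example through team-level or non-random allocation). The additive estimate is biased by the full 0.3. Baseline adjustment is biased by 0.3(1−ρ) = 0.15/0.09/0.03. Change scores are unbiased.

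*Chance imbalance* (individual randomisation, with an observed baseline difference of 0.3). The post-season difference regresses to 0.3ρ. The conditional mean is then 0 for baseline adjustment, −0.3(1−ρ) for change scores and 0.3(1+ρ)/2 for the additive term. Example for change scores at ρ = 0.5: mean −0.15, conditional SE 0.1414, critical value 1.96 × 0.1633 = 0.320, so rejection ≈ Φ((−0.320 + 0.15)/0.1414) = Φ(−1.20) ≈ 0.115.

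| Rejection rate, ρ 0.5/0.7/0.9 | Systematic | Chance |
|---|---|---|
| Additive | 56%/51%/47% | about 23%/25%/22% |
| Baseline-adjusted | 19%/12%/7% | 5%/5%/5% |
| Change score | 5%/5%/5% | about 12%/9%/6% |

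The two longitudinal analyses change places between the columns.

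**Step 4: correlation (secondary).** Suppose the impact slope is 0.3 in both arms, so there is no protection. Each arm of 75 has power of about Φ(atanh(0.3)·√72 − 1.96) = Φ(2.626 − 1.960) = 0.747. Exactly one arm is then significant with probability 2 × 0.747 × 0.253 = 0.378; simulation gave 0.371, with the no-collar arm alone significant in 0.178. The arm-by-exposure test rejected in 0.050.

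**The case against.** The strongest reply is that the intent is plain. The Abstract and Purpose of Study describe longitudinal change, the group-by-time form is written for reaction time, and the football study under Summary of Prior Work compared arms directly on pre- to post-season diffusion change. A model with two two-level factors is a strained account of the term analysis of covariance, and the list of candidate predictors does not claim to be complete. Between the two plausible longitudinal readings the power gap is modest: 94% against 87% at ρ = 0.5, and 99% against 98% at 0.7. All of that stands. It makes a longitudinal analysis the likelier intent, but it does not put one into the imaging plan.

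Three stronger readings might be inferred, and the documents do not support them.

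- *The trial has only 35-42% power for imaging.* Those figures belong to the literal additive reading alone, under assumed inputs.
- *Baseline imbalance would produce a false positive in about half of trials.* The 56%/51%/47% figures need a systematic difference, which individual randomisation excludes; for a chance imbalance they are about 23%/25%/22%.
- *The second aim has no between-arm analysis.* That aim does not name imaging, and the Poisson model compares arms on rates, "using an offset to account for the playing time and exposure to concussive impact for each of the study participants". The correlation is described only as a test of association, and nothing says that it will be reported as evidence of protection.

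The unit of allocation and team clustering are a separate issue. Clustering would lower every power shown, but adds no weight to this point.

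**Conclusion.** The point holds as an incomplete specification of the imaging comparison. The documents contain no pre-season covariate, change score or group-by-time term for imaging, and confidence in that omission is high. The size of the consequence is conditional. With 75 per arm, individual randomisation, equal allocation and a 0.5 SD effect, the literal model estimates 0.25 SD with 42%/38%/35% power, against 94%/99%/>99% baseline-adjusted and 87%/98%/>99% for group-by-time. It does not follow that the investigators will run the literal model. It should be fixed because imaging is a basis for judging effectiveness and the remedy costs almost nothing. The handling of arm in the imaging-impact correlation is a real but secondary gap.

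**What to change.** For imaging outcomes only, replace the ANCOVA sentence with: post-season value = arm + pre-season value, one row per athlete; arm difference with 95% CI. State the change-score (group-by-time) analysis as sensitivity. Applying the form in the Simple Reaction Time section to imaging is an acceptable smaller edit that also removes the ambiguity. The reaction-time and oculomotor sections need no change on this point.

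Cost: a few lines of text, using data already planned. The trade-off should be stated with its label. If groups differ systematically by 0.3 SD at baseline with no effect on change, baseline adjustment rejects in 19%/12%/7% of trials against 5% for change scores. Under individual randomisation, a chance imbalance of that size leaves baseline adjustment at 5% and change scores at about 12%/9%/6%. Hence one analysis is named as main and the other as sensitivity.

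Secondary: if the correlation is to support protection, add centred cumulative impact exposure and arm × exposure to the pre-season-adjusted model in a separate supportive analysis. Report the interaction with its 95% CI, and do not infer protection from significance in one arm only. Two limits should be stated. Exposure accrues after assignment, so this is not a purely randomised contrast. It is also imprecise: at 75 per arm the half-width is about 1.96·√(2(1−ρ²)/75) = 0.28/0.23/0.14 SD per SD of exposure, and power for a slope difference of 0.3 is about 56%/73%/99%. The arm effect for the first aim should come from the main model, not from this one.
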